k/ Errands							
• Work/							
Studies							
	1	2	3	4	5		

Table 45D- Itch Questionnaire

5. Distribution	Mark whether itching has been present in the following part of your body over the last 2 weeks. If a body part is not listed choose the one that is closest anatomically								
Head/ Scalp		Top of feet/ Toes							
Face		Soles							
Chest		Palms							
Abdomen		Top of hands/ fingers							
Back		Forearms							
Buttocks		Upper arms							
Thighs		Point of contact w/ clothing							
Lower Legs		Groin							

- Mean change in Skindex-10 (Domain Scores and Total Score) from Baseline to Week 4, Week 8 and Week 12
 - The Skindex-10 consists of 10 questions (beginning with "During the past week, how often have you been bothered by.....") exploring the impact of itch on 3 domains (disease, mood/emotional distress and social functioning) with a 1 week recall period.
 - Each question must be scored on a 7-point scale ranging from 0 (never bothered) to 6 (always bothered).
 - The domain scores are the sums of the following: disease domain (questions 1 to 3), mood/emotional distress domain (questions 4 to 6), and social functioning domain (questions 7 to 10).
 - The total score is the sum of the numeric value of each answered question. The total score ranges from 0 to 60.
 - Continuous descriptive statistics will be presented for individual questions (Q1- Q10).
 - Domains (1) Disease (Q1- Q3), Domain (2) Mood/ Emotional Distress (Q4 Q6) and Domain (3) Social Functioning (Q-7 - Q10) will be presented using continuous descriptive statistics.
 - Mean change in Total Skindex-10 Score will be summarized descriptively from Baseline to Week 4, Week 8 and Week 12.

Durin	During the past week, how often have you been bothered by:										
		0	1	2	3	4	5	6			
		(Never						(Always			
		bothered)						bothered)			
1.	Your itching										
2.	The										
	persistence/										
	reoccurrence of										
	your itching										
3.	The appearance										
	of your skin										
	from scratching										
4.	Frustration										
	about your										
	itching										

Table 5Skindex-10 Questionnaire

5. Being annoyed about your itching				
6. Feeling depressed about your itching				
7. Feeling embarrassed about your itching				
8. The effects of your itching in interactions with other				
9. The effects of your itch on your desire to be with people				
10. The effect of your itching making hard to work or do things you enjoy				

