5.2 Handling of Dropouts or Missing Data

5.2.1 Missing Data

For the primary and secondary efficacy endpoints, the primary estimands using the FAS, MFAS and PPS will use a treatment policy strategy for missing data. Missing data will be replaced using a multiple imputation (MI) approach. Note, missing data includes dropouts, empty data fields after dropout date will be handled as missing data regardless of reason for drop out. MI will be performed for all populations separately only if there is a difference in populations. Seed numbers for each endpoint will use the randomly generated 4-digit numbers from the table below. Other variables that are included in the imputation model will include treatment, site, country, visit, and key baseline characteristics such as age, gender, race, CKD stage stratum⁽¹⁾ at baseline, and systemic CKD-aP treatment status⁽²⁾ at baseline. Depending on the pattern of missingness, a 2-step process may be employed. If missing data points occur for an intermediate visit, they will be imputed first using a Markov Chain Monte Carlo (MCMC) method. As a result, a monotone missingness pattern will be obtained for the data to be fully imputed. The subsequent imputation will use general regression for continuous variables and logistic regression for categorical variables under the assumption data are missing at random to produce 20 imputed datasets where the remaining missing data are filled in using 20 separate sets of values. For the categorical secondary variables, the percentages will be calculated from the above imputed data.

- (1) CKD stage stratum at baseline= A. ≥40% of subjects must be on dialysis (HD or HDF) and must be CKD stages 4-5 (CKD stage 4-5 dialysis) B. ≥20% of subjects must Not be on dialysis and must be CKD stages 4-5 (CKD stage 4-5 non-dialysis) C. ≥20% of subjects must Not be on dialysis and must be CKD stage 3 (CKD stage 3)
- (2) Systemic CKD-aP treatment status at baseline will be flagged as "Yes" if prior/concomitant medication falls within one of the ATC groups provided in Section 6.3.2

Table 9 Population and Random Seed Number

Population	Random Seed Number
FAS	6529
MFAS	7631
PPS	9376

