5.2.4 COVID-19 Impacted Visits

Since the primary and secondary efficacy endpoints are derived from the subjects' diaries and summaries of other efficacy endpoints and safety endpoints are as observed, there will be no adjustments made for coronavirus disease of 2019 (COVID-19) impacted visits.

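### The Skindex-10 total sums answered questions only, so a blank item scores the same as never bothered and can distort change from Baseline in either direction

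*SAP*

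**What the plan says.** SAP 3.4 describes the instrument in these terms: "The Skindex-10 consists of 10 questions", each item scored from 0 (never bothered) to 6 (always bothered). The total is defined by "The total score is the sum of the numeric value of each answered question", followed by "The total score ranges from 0 to 60". Protocol 7.9.6.1 gives the same rule and the same range.

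The three domain scores are plain sums over questions 1 to 3, 4 to 6 and 7 to 10. The word answered is attached to the total and not to the domains, for which neither document says what happens to a blank item.

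The endpoint is "Mean change in Skindex-10 (Domain Scores and Total Score) from Baseline to Week 4, Week 8 and Week 12". It is listed among the other efficacy endpoints and is summarised descriptively (SAP 3.4 and 5.5.3).

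Multiple imputation does not reach it. SAP 5.2.1 is framed for a different set of endpoints: "For the primary and secondary efficacy endpoints, the primary estimands using the FAS, MFAS and PPS will use a treatment policy strategy for missing data". SAP 5.2.4 states that "summaries of other efficacy endpoints and safety endpoints are as observed". Neither document sets an incomplete Skindex-10 form to missing, requires a minimum number of answered items, or pro-rates.

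**The concern.** On this scale 0 is the best possible answer. A rule that adds up whatever was answered gives every blank item the value 0, so a partly completed form looks like a form with less bother. In a change score, this produces false improvement when the blank falls after Baseline and false worsening when it falls at Baseline.

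The rule also departs from the SAP's own practice. For the diary itch score, SAP 3.1 averages the available values, requires at least 4 of the 8 expected, and otherwise sets the weekly mean to missing. Skindex-10 has neither the averaging nor the minimum: a form with one answered item would still yield a total, of at most 6 out of 60.

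At stake is the descriptive comparison of the arms on one of the three quality-of-life instruments in Protocol 7.9.6. No hypothesis test is involved.

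**Working it through.** **Inputs.** Ten items scored 0 to 6, domains of 3, 3 and 4 items, and total equal to the sum of answered items (SAP 3.4, Protocol 7.9.6.1). Planned arms are 72 and 36 (Protocol 8.2). The item skip rate is not given in either document and is assumed below.

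**The stated range.** 10 × 0 = 0 and 10 × 6 = 60; by domain, 18 + 18 + 24 = 60. The 0 to 60 range is reproduced for a complete form. With k items blank, the largest attainable total is 6 × (10 − k): 54 for one blank and 48 for two.

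**One subject, no true change.** Apparent change = −(sum of true scores of items blank only after Baseline) + (sum of true scores of items blank only at Baseline).

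For a subject at 4 on every item at both visits:

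| Blank items | Baseline total | Week 12 total | Apparent change |
|---|---|---|---|
| None | 40 | 40 | 0 |
| One, Week 12 only | 40 | 36 | −4 |
| Two, Week 12 only | 40 | 32 | −8 (20% of 40) |
| Two, Baseline only | 32 | 40 | +8 |
| Same two, both visits | 32 | 32 | 0 |

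Each item blank only after Baseline costs its true score: 0 if that score is 0, and at most 6. Two such blanks cost at most 12. An item blank at both visits contributes nothing to the change, so any real change on it is lost.

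**Arm level (assumed rates).** If a fraction f of an arm skips one item with true score s after Baseline only, the mean change shifts by −f × s.

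- Low end: 0.05 × 3 = 0.15, a shift of −0.15.
- High end: 0.20 × 6 = 1.2, a shift of −1.2.
- Unequal skipping, 20% in one arm and 5% in the other with s = 4: (0.20 − 0.05) × 4 = 0.6 points in the between-arm difference, in favour of the arm that skips more.
- Equal f and s in both arms: the shift cancels in the difference but stays in each arm's reported mean change.

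For scale, one subject with the 8-point error moves the mean of an arm of 72 by 8/72 = 0.11 and of an arm of 36 by 8/36 = 0.22.

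**Effect of pro-rating.** With the mean of answered items × 10, the subject at 4 who skips two items scores 32/8 × 10 = 40, a change of 0. More generally, for one blank item with true score s, where the nine answered items average m, the true total is 9m + s. The sum rule returns 9m, an error of −s. Pro-rating returns 10m, an error of m − s. Pro-rating therefore removes the systematic pull towards 0, but it is exact only when the blank item resembles the others.

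**The case against.** Several points on the other side stand.

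- **The stakes are low.** Skindex-10 has no test, model or p-value and plays no part in the primary or secondary endpoints.
- **The problem would be partly visible.** SAP 3.4 calls for summaries of each of the ten questions, and SAP 5.1 includes the number of non-missing values in continuous summaries. By-arm, by-visit tables would show item non-response, although they would not correct the totals.
- **Completion is expected.** The SAP says "Each question must be scored on a 7-point scale ranging from 0 (never bothered) to 6 (always bothered"), and patient-reported outcomes come first at in-clinic visits (Protocol 7.9). This is a completion instruction, and it may keep blanks rare. It does not say how to score one, and the scoring rule itself allows for unanswered questions.
- **The developer's scoring guide is not in the documents.** Whether the written rule is the developer's own cannot be checked here.

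Three stronger readings are tempting and are not supported.

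- A reader might infer that skipping always looks like improvement. The direction depends on which visit has the blank.
- A reader might infer that the domains suffer the same stated error, so that one blank social item takes a subject at 4 from 16 to 12. The sum-of-answered wording covers only the total. For the domains the rule is undefined, and a blank could equally make the domain missing.
- A reader might expect subjects to leave the work and social items blank as not applicable. Nothing in either document says so, and the tenth item covers enjoyable activities as well as work.

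**Conclusion.** The point holds for the total score and is minor. As written, a blank item is scored as the best answer, which is inconsistent with treating every total as lying on a 0 to 60 scale. Nothing elsewhere in the protocol or SAP overrides the rule.

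The error is up to 6 points per blank item for a subject. At arm level it is about −0.15 to −1.2 points of 60, if 5% to 20% of subjects skip one item with a true score of 3 to 6 after Baseline only. Those rates are assumptions; with few blanks the effect is negligible. The between-arm difference is affected only if skipping, or the scores of the skipped items, differ by arm. For the domains, the finding is limited to the absence of a rule for blank items.

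**What to change.** Before unblinding, amend SAP 3.4 so that:

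- the Skindex-10 total is computed only when a pre-specified minimum of items is answered, for example at least 8 of 10, as the mean of answered items × 10, and is otherwise missing;
- the domain scores follow one stated rule of the same kind, with a minimum number of answered items and pro-rating to the domain's number of items, otherwise missing;
- the SAP says what is reported when the total qualifies but a domain does not. For example, a form with two of the three disease items blank still has 8 of 10 answered.

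The 8 of 10 cut-off is an illustration and comes from neither document. If the developer's scoring guide gives a missing-item rule, compare it with the chosen rule and explain any difference. Because Protocol 7.9.6.1 carries the same scoring rule, record the change in SAP 6.2.

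The cost is a few sentences in the SAP and a small programming change, with no new data. The downside is that a few totals become missing, and pro-rating assumes that a blank item resembles the answered ones.

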- Mean change in EQ-5D-5L (Visual analogue scale [VAS] and Index value) from Baseline to Week 4, Week 8 and Week 12

Note: EQ-5D-5L Index Value (calculated using EQ5D5L algorithm) and VAS (i.e., Your Health Today Question) will be analyzed separately.

EQ-5D-5L Index Value:

The EQ-5D-5L descriptive system comprises five dimensions (5D) (MOBILITY, SELF-CARE, USUAL ACTIVITIES, PAIN / DISCOMFORT and ANXIETY / DEPRESSION), each dimension has five response levels (5L): no problems, slight problems, moderate problems, severe problems, unable to/extreme problems. The respondent is asked to indicate his/her health state by checking the box next to the most appropriate response level for each of the five dimensions.

A unique health state is defined for each subject by combining the response levels from each of the five dimensions. EQ-5D-5L health states can thus be summarized using the 5-digit code summary number, which reflects how good or bad a health state is according to the preferences of the general population of a country/region.

To compare two or more health states with each other or to understand which dimension has a greater impact on health-related quality of life (HRQoL), an index value derived from a set of utility values is given to each unique health state. This index value is needed to summarize how good or bad each health state is on a scale anchored at 1 (full health) and 0 (a state equivalent

to dead). Values less than 0 represent health states considered to be or modelled as worse than dead.

The utility values are based on the views and preferences of the general public and numerous country-specific value sets were produced by EuroQol Research Organization for EQ-5D-5L. The EQ-5D-5L index value for this study will be calculated for patients in United Kingdom using English Population Value Set, and for Germany, Hungary and Poland, using German population value set, Hungarian population value set, and Polish population value set respectively as presented in Table 6.

An index value thus calculated based upon below mentioned value sets can range anywhere between -1 and 1.

Table 6	EQ 5D 5L Values sets for U	Jnited Kingdom (UK),	Germany (GR), Hungary (HR)
and Poland (I	PL)		

Activity	Scale	Score	UK Value	GR Value	HR Value	PL Value
			Set	Set	Set	Set
Mobility	I have no problem in walking	1	0	0	0	0
	I have slight problem in walking	2	0.058	0.026	0.035	0.025
	I have moderate problem in walking	3	0.076	0.042	0.054	0.034

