	I have severe problem in walking	4	0.207	0.139	0.174	0.126
	I am un able to walk	5	0.274	0.224	0.192	0.314
 	x 1 1 1 1	1				0
Self Care	I have no problem in washing or dressing myself	1	0	0	0	0
	I have slight problem in washing or dressing myself	2	0.050	0.050	0.045	0.031
	I have moderate problem in washing or dressing myself	3	0.080	0.056	0.044	0.047
	I have severe problem in washing or dressing myself	4	0.164	0.169	0.152	0.111
	I am un able to wash or dress myself	5	0.203	0.260	0.125	0.264
Usual Activity	I have no problem in performing usual activities	1	0	0	0	0

	I have slight problem in performing usual activities	2	0.050	0.036	0.035	0.023
	I have moderate problem in performing usual activities	3	0.063	0.049	0.050	0.040
	I have severe problem in performing usual activities	4	0.162	0.129	0.132	0.097
	I am un able to perform usual activities	5	0.184	0.209	0.059	0.205
Pain/ Discomfort	I have no pain and discomfort	1	0	0	0	0
	I have slight pain and discomfort	2	0.063	0.057	0.043	0.030
	I have moderate pain and discomfort	3	0.084	0.109	0.030	0.050
	I have severe pain and discomfort	4	0.276	0.404	0.215	0.261
	I am extreme pain and discomfort	5	0.335	0.612	0.123	0.575
Anxiety/ Depression	I have no anxiety/ depression	1	0	0	0	0
	I have slight anxiety/ depression	2	0.078	0.030	0.040	0.018
	I have moderate anxiety/ depression	3	0.104	0.082	0.053	0.029
	I have severe anxiety/ depression	4	0.285	0.244	0.168	0.108
	I have extreme anxiety/ depression	5	0.289	0.356	0.079	0.232

Overall Utility Value Total (UVT)= Mobility UVT+ Self Care UVT+ Usual Activity UVT+ Pain/ Discomfort UVT + Anxiety/ Depression (UVT) **EQ5D5L Index=** 1, Overall UVT (rounded to three desired points)

EQ5D5L Index= 1- Overall UVT (rounded to three decimal points)

EQ-5D-5L VAS Score

The VAS records the subject's overall current health on a vertical VAS where the endpoints are labelled "(100) The best health you can imagine" and "(0) The worst health you can imagine." The VAS provides a quantitative measure of the subject's perception of his/her overall health, higher score indicating better quality of life.

Table 7EQ-5D-5L VAS

Your Health	On a rate of 0 to 100 how is your health today, 0 being worst	0 - 100
today	and 100 being best	

Mean change in EQ-5D-5L Index score and VAS score will be presented descriptively from Baseline to Week 4, Week 8 and Week 12.

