6.3 Reference Materials

6.3.1 EQ-5D-5L Index Value

The EQ-5D-5L descriptive system comprises five dimensions (5D). The respondent is asked to indicate his/her health state by checking the box next to the most appropriate response level for each of the five dimensions.

A unique health state is defined for each subject by combining one level from each of the five dimensions. A total of 3125 possible unique health states is defined in this way. Each state is referred to by a 5-digit code.

For example, working clockwise from the top of the diagram, state 12345 indicates no problems with mobility, slight problems with washing or dressing, moderate problems with doing usual activities, severe pain or discomfort and extreme anxiety or depression, while state 11111 indicates no problems on any of the five dimensions and 55555 indicates extreme problems at each dimension.

EQ-5D-5LUserGuide Basic information on how to use the EQ-5D-5L instrument Version3.0

https://euroqol.org/eq-5d-instruments/eq-5d-51-about/valuation-standard-value-sets/

Parallel Valuation of the EQ-5D-3L and EQ-5D-5L by Time Trade-Off in Hungary

DOI link: https://doi.org/10.1016/j.jval.2020.03.019

Published Print: 2020-09

Valuation of EQ-5D-5L Health States in Poland: the First EQ-VT-Based Study in Central and Eastern Europe

Crossref DOI link: https://doi.org/10.1007/s40273-019-00811-7

Published Print: 2019-09

Value Sets for EQ-5D-5L- A Compendium, Comparative Review & User Guide

https://doi.org/10.1007/978-3-030-89289-0

Valuing health-related quality of life: An EQ-5D-5L value set for England

DOI: 10.1002/hec.3564

German Value Set for the EQ-5D-5L

https://doi.org/10.1007/s40273-018-0615-8

6.3.2 Systemic treatment CKD-aP can be identified via ATC code Level 3 or 4:

R06A Antihistamines for systemic use
R06AA Aminoalkyl ethers
R06AB Substituted alkylamines
R06AC Substituted ethylene diamines
R06AD Phenothiazine derivatives
R06AE Piperazine derivatives
R06AK Combinations of antihistamines
R06AX Other antihistamines for systemic use
H02A Corticosteroids for systemic use, plain
H02B Corticosteroids for systemic use, combinations
For some of them only Level 4 could be the most specific:
N02BF Gabapentinoids
N02BG Other analgesics and antipyretics

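### SAP Table 6: in the Hungarian EQ-5D-5L column, level 5 costs less than level 4 in four of five dimensions, so state 55555 scores 0.422 and 44444 only 0.159

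*SAP*

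**What the plan says.** Protocol section 4.2 lists change in EQ-5D-5L to Week 12 among the other endpoints, and Protocol section 7.9.6.3 states that a higher index means better quality of life. SAP section 3.4 gives the scoring. Subjects in the UK, Germany, Hungary and Poland each get their own national set; for the last two the text reads "Hungarian population value set, and Polish population value set respectively as presented in" Table 6. The total is defined as "Overall Utility Value Total (UVT)= Mobility UVT+ Self Care UVT+ Usual Activity UVT+ Pain/ Discomfort UVT + Anxiety/ Depression (UVT)", and the index follows as "EQ5D5L Index= 1- Overall UVT (rounded to three decimal points)". Each dimension therefore contributes one tabulated value, with no accumulation over levels and no extra term.

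The value columns of Table 6 run UK, Germany, Hungary (headed HR), Poland. The pain rows for levels 4 and 5 read "I have severe pain and discomfort 4 0.276 0.404 0.215 0.261" and "I am extreme pain and discomfort 5 0.335 0.612 0.123 0.575". SAP section 6.3.1 explains the state codes, noting that "55555 indicates extreme problems at each dimension", and lists the source papers, including "Parallel Valuation of the EQ-5D-3L and EQ-5D-5L by Time Trade-Off in Hungary". On reporting, section 3.4 says: "Mean change in EQ-5D-5L Index score and VAS score will be presented descriptively from" Baseline to Weeks 4, 8 and 12.

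**The concern.** Because the index is 1 minus a plain sum of decrements, a more severe level must have a decrement at least as large as the level below it. In the pain rows, the third value drops from 0.215 at severe to 0.123 at extreme, while the other three countries rise. If the same happens in other dimensions, the Hungarian index can move the wrong way: some subjects who get better are recorded as worse, and some who get worse as better. Since SAP section 5.1 pools all centres, these values would enter the overall mean changes, and a descriptive table would give no sign of it.

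**Working it through.** **Inputs.** Hungarian (HR) column of SAP Table 6; level 1 is 0 throughout.

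| Dimension | Level 2 | Level 3 | Level 4 | Level 5 | Falls |
|---|---|---|---|---|---|
| Mobility | 0.035 | 0.054 | 0.174 | 0.192 | none |
| Self-care | 0.045 | 0.044 | 0.152 | 0.125 | 2→3, 4→5 |
| Usual activities | 0.035 | 0.050 | 0.132 | 0.059 | 4→5 |
| Pain/discomfort | 0.043 | 0.030 | 0.215 | 0.123 | 2→3, 4→5 |
| Anxiety/depression | 0.040 | 0.053 | 0.168 | 0.079 | 4→5 |
| Sum | 0.198 | 0.231 | 0.841 | 0.578 | |

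Five dimensions with four adjacent level pairs each give 20 pairs; 6 of them fall. In the other three columns, 0 of 60 pairs fall.

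**Index for uniform states** (1 minus the column sum). The SAP prints no worked index value to reproduce, so these come directly from its formula.

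- 22222: 1 − 0.198 = 0.802
- 33333: 1 − 0.231 = 0.769
- 44444: 1 − (0.174 + 0.152 + 0.132 + 0.215 + 0.168) = 1 − 0.841 = 0.159
- 55555: 1 − (0.192 + 0.125 + 0.059 + 0.123 + 0.079) = 1 − 0.578 = 0.422

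The worst possible state therefore scores 0.422 − 0.159 = 0.263 above 44444. In the other columns the order is as it should be:

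| Set | 44444 | 55555 |
|---|---|---|
| UK | −0.094 | −0.285 |
| Germany | −0.085 | −0.661 |
| Poland | 0.297 | −0.590 |

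**All states.** Scoring all 5^5 = 3125 states per country, the minimum is at 55555 in the UK, Germany and Poland. In Hungary it is at 54444: 1 − (0.192 + 0.152 + 0.132 + 0.215 + 0.168) = 0.141. There, 247 states score below 55555.

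**Effect of a one-level improvement in one dimension** (old decrement minus new decrement; a correct table gives zero or a positive number).

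- Level 5 to 4, self-care: 0.125 − 0.152 = −0.027
- Level 5 to 4, usual activities: 0.059 − 0.132 = −0.073
- Level 5 to 4, anxiety/depression: 0.079 − 0.168 = −0.089
- Level 5 to 4, pain/discomfort: 0.123 − 0.215 = −0.092
- Level 3 to 2, self-care: 0.044 − 0.045 = −0.001
- Level 3 to 2, pain/discomfort: 0.030 − 0.043 = −0.013

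**One possible cause, not shown by the documents.** The entries may be level-to-level increments that should be cumulated. On that assumption the cumulated sums are 0.198, 0.198 + 0.231 = 0.429, 0.429 + 0.841 = 1.270 and 1.270 + 0.578 = 1.848, giving 0.802, 0.571, −0.270 and −0.848 for 22222 to 55555. Any positive numbers become ordered once cumulated, so this is no evidence for the reading; only the source paper can settle it.

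**The case against.** The reversal is not general: 14 of the 20 Hungarian pairs rise, and the two falls between levels 2 and 3 are small (0.001 and 0.013). The large ones need a level 5 response, and the documents give no EQ-5D distribution from which to judge how often that occurs. The index has no model, test or imputation (SAP section 5.5.3 has descriptive summaries only). The same column serves both arms, so the error is not tied to treatment. A programmer might also work from the published Hungarian set, which the SAP names and cites, and never reproduce the printed column.

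All of this limits the reach, and it stands. It does not remove the fault. The SAP directs use of the values printed in Table 6 and prints the formula. Neither section 6.2 (changes from the protocol) nor section 6.3.1 corrects the column or adds an accumulation rule. An error common to both arms can still distort an observed difference between them. Damage in the conversion from PDF is an unlikely explanation: each row for levels 2 to 5 holds four values in sequence, and the three other columns are correctly ordered throughout.

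**Conclusion.** The point holds. Followed as written, SAP section 3.4 scores an improvement from level 5 to level 4 in a Hungarian subject as a worsening in four of five dimensions, by 0.027 to 0.092, and an improvement from level 3 to level 2 as a worsening in two, by 0.001 and 0.013. It also ranks 55555 above 44444 by 0.263. This rests only on the printed values, the printed formula and the rule that a higher index is better. It is certain as to the reversal, not as to its cause. The consequence is limited to the EQ-5D-5L index in Hungarian subjects and to pooled summaries that include them. How much a pooled mean would shift cannot be computed, because neither the number of Hungarian subjects nor their response levels are given. It should be fixed, but it does not touch the trial's main conclusions.

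**What to change.** Before the index is calculated, compare the Hungarian column of Table 6, and the rule for combining its values, with the valuation paper cited in SAP 6.3.1. Correct whichever is wrong. If the entries prove to be increments, replace them with cumulated decrements so that one formula serves all four countries. Add a check to the scoring program that, in every country and dimension, the decrement never falls as the level rises, and that 55555 is the lowest-scoring state. If the index has already been produced, rerun it and document the correction in the clinical study report. The cost is one table column and one program; no collected data and no other endpoint change.
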